A plan is in place for identifying and referring individuals who report significantly worsening alcohol use trajectories as well as consumption of potentially lethal doses of alcohol (BAC's above .35) and potential for alcohol use disorder as measured on the AUDIT. Specifically, the baseline, 1-month, and 6-month surveys will be screened immediately upon submission for indication of significant risk based on criteria established in our prior trials of this nature and the research literature (i.e., a score of 8 or more (age 18-25)/a score of 4 or more (age 15-17) on the AUDIT on baseline, 1-month, or 6-month surveys in combination with a BAC in the past month exceeding .35%; Chung et al., 2000; 2002). The AUDIT total score is used to assess the risk of alcohol use disorder. A score of 8 or more is suggested for identifying hazardous drinking behaviors among adults, and a score of 4 or more is suggested for identifying hazardous drinking behaviors among adolescents as young as 13. Thus, both outcomes (8+AUDIT and 4+AUDIT, respectively) will be used to assess hazardous alcohol use for referral in combination of .35% BAC. Participants who meet this criterion will be emailed local referral information. All such contact will be noted in the tracking database. In our ongoing trials, we have used this procedure without incident. Information regarding the potential for a follow-up contact by the investigators to clarify responses or provide information is included in the consent documents. Participants are also informed in the Informed Consent that they are free to seek other services for their alcohol use. This structure is currently in place and approved at both the local and federal level on all our existing drinking and health-risk behavior studies. **All participants (parents and teens), at the end of participation, will be provided with referral resources available both locally and nationally.**

If an adolescent in the study reports significantly worsening alcohol use trajectories or consuming potentially lethal doses alcohol, their parents will not be informed about this report due to confidentiality.

See Referral Information Email in Appendices.

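### The referral trigger requires an AUDIT cut-off as well as a BAC above .35%, so a BAC the protocol calls potentially lethal does not prompt a referral email on its own

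*Combined protocol and SAP*

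**What the plan says.** Item 4 of section G (risks or discomforts) introduces the safeguard in these words: "A plan is in place for identifying and referring individuals who report significantly worsening alcohol use trajectories". The same sentence goes on to name "consumption of potentially lethal doses of alcohol (BAC's above .35) and potential for alcohol use disorder as measured on the AUDIT". Item 2 of section G repeats the commitment for worsening use and potentially lethal doses, without any AUDIT condition, and treats this screening as a potential direct benefit of taking part.

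Item 4 then gives the operating rule. Each of the three surveys "will be screened immediately upon submission for indication of significant risk". On where the rule comes from, the protocol says that this screening is "based on criteria established in our prior trials of this nature and the research literature". The criterion is an AUDIT score of at least 8 (ages 18-25) or at least 4 (ages 15-17) "on the AUDIT on baseline, 1-month, or 6-month surveys in combination with a BAC in the past month exceeding .35" per cent. It is restated a few lines later: "Thus, both outcomes (8+AUDIT and 4+AUDIT, respectively) will be used to assess hazardous alcohol use for referral in combination of .35% BAC". The action follows: "Participants who meet this criterion will be emailed local referral information".

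Section G also describes other routes to help. Referral information is offered to anyone who expresses interest in help, participants are told where services can be found, and everyone receives local and national resources on finishing. The protocol adds: "Information regarding the potential for a follow-up contact by the investigators to clarify responses or provide information is included in the consent documents".

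**The concern.** The protocol itself labels a BAC above .35 potentially lethal and says that people who report it are referred. The rule that sends the email adds a second condition of a different kind. By the protocol's own description, the AUDIT total measures risk of alcohol use disorder, whereas the BAC describes a dose. A survey flag programmed as written would pass over a dangerous dose reported by someone whose AUDIT score is low.

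Such a person could be enrolled. The inclusion criteria in section F require no drinking history, and section E item 1 lists alcohol initiation among the outcomes, so the sample may contain new drinkers. How often the combination occurs is unknown.

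A secondary point of wording is that the opening of item 4 refers to worsening use, while the rule looks only at levels.

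**Working it through.** The protocol gives no figure for this rule, so there is none to reproduce. The check is on its logic and its timing.

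**Inputs**
- AUDIT cut-offs, BAC limit, way of combining them and the resulting action: section G item 4.
- Commitment without an AUDIT condition: section G item 2.
- Survey times of 0, 1 and 6 months: section A (Aim 2). Overall duration of 6 months: section E item 5.

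**Step 1: the rule as logic.** Let A = AUDIT at or above the cut-off, B = past-month BAC above .35%, W = use has worsened. The stated rule is: email if A AND B. The wording that joins the two conditions appears twice, and the email goes to those meeting a single criterion. The supplied text gives no support for reading it as A OR B.

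**Step 2: what the rule flags.** Three yes/no conditions give 2 × 2 × 2 = 8 patterns. These are patterns, not shares of participants.

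| Rule | Patterns flagged |
|---|---|
| A AND B (as written) | 2 of 8 |
| B alone sufficient | 4 of 8 |

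The difference, 4 − 2 = 2 patterns, is B without A, with or without W: a potentially lethal BAC and a low AUDIT score.

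**Step 3: same survey or not.** The text does not say that A and B must come from the same survey, although that is the natural reading. On that reading, anyone with B but not A at a given survey is not flagged then. If values from different surveys could be combined, someone whose AUDIT stays below the cut-off at every survey would still never be flagged.

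**Step 4: worsening.** W does not appear in the rule; there is no change score and no comparison with an earlier survey. However, the rule is applied afresh at each survey. A participant below the joint threshold at baseline and above it at 1 or 6 months is flagged at that later survey. The rule misses worsening that never reaches the joint threshold.

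**Step 5: the wait.** A participant who meets the rule can be emailed once the survey is screened. For a participant with B but not A, the longest wait for the resources given to everyone on finishing is:
- baseline report: 6 − 0 = 6 months
- 1-month report: 6 − 1 = 5 months
- 6-month report: 6 − 6 = 0 months

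These are upper limits. They assume that participation ends with the 6-month survey, that no later survey meets the rule, and that no other route is used. A baseline case that meets the rule at the 1-month survey would wait about 1 − 0 = 1 month.

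**The case against.** The strongest reply is that the joint criterion is deliberate. The protocol attributes it to earlier trials and to literature, and reports that the procedure has been used without incident and that the structure is approved locally and federally. The opening sentence can fairly be read as a general description that the rule then makes precise. Other routes to help exist, and the consent documents mention possible investigator contact. What is lost is one email, and perhaps nobody falls in the gap.

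Much of this stands. The cited sources are not available here, so nothing shows the joint rule to be clinically wrong. The affected number could be zero. The reply does not explain why a dose called potentially lethal, and listed for referral in item 2 with no AUDIT condition, should need a second condition. None of the other routes is stated to be triggered by a reported BAC, and the sentence on follow-up contact names no trigger.

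Two stronger readings are tempting. A reader might infer that worsening use is never detected; the repeated screening contradicts this, since a rise into the joint threshold is caught. A reader might also infer that a missed participant is left without help for half a year. The documents do not support that either: 6 and 5 months are upper limits, and section G item 4 promises information on where to find services, in a passage that follows directly on the informed consent process and so may apply before any survey.

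**Conclusion.** The point holds and is minor. The trigger is narrower than the purpose the protocol states for it: a past-month BAC above .35% with an AUDIT score below the cut-off at that survey prompts no referral email. The number of participants affected is unknown. The delay to the resources given to everyone is at most about 6 months (baseline report) or 5 months (1-month report), on the assumptions listed with the calculation.

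The mismatch on worsening use is one of wording. So is the opening sentence's listing of AUDIT-defined risk as if it were referred separately. A reader might also infer from the 18-25 age band that older parents have no cut-off, but the following text applies a score of 8 to adults generally, so that is clerical.

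The conclusion rests on the rule in section G item 4 being the whole rule, as it is presented. The consent form, the referral email, the other appendices and a stretch of text after the start of the compensation schedule in section H were not available, so a separate rule there cannot be excluded. Sample size, power and the planned analysis are unaffected.

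**What to change.** Make a past-month BAC above .35% sufficient on its own for the referral email. This removes one condition from the survey flag and changes a sentence or two in section G item 4. It needs no new data, because the rule already uses past-month BAC from surveys screened on submission.

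The cost is some additional mid-trial emails, likely few but not computable from the documents. Emails sent after the baseline or 1-month survey could slightly affect later reported drinking, and teen alcohol use is a primary outcome (section E item 1). Contacts of this kind are already logged in the tracking database, so they can be counted and described.

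As a wording change, revise the references to significantly worsening use in section G items 2 and 4 so that they describe what the rule does, namely flag a level at each survey. This adds no contacts.
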